3.1.1.1 BMS-986183 Dose Escalation (Part 1)

In BMS-986183 dose escalation (Part 1), BMS-986183 monotherapy will be administered Q3W (21 days/cycle), and BMS-986183 dose expansion (Part 2) may be initiated once the MTD or a tolerated dose below the MTD for BMS-986183 dose escalation (Part 1) is established.

BMS-986183 Dose Escalation (Part 1): (BMS-986183 administered every 3 weeks)

Approximately 30 subjects will be enrolled in ascending dose level cohorts starting with a flat dose of 3 mg (0.05 mg/kg based on a 60 kg body weight individual) of BMS-986183 monotherapy. BMS-986183 monotherapy will be administered Q3W in a 21-day cycle. The approach for selection of the next dose at each escalation step is presented below. For the rules for escalation decision based on DLT criteria, see Section 4.5.1.

BMS-986183 Dose Escalation (Part 1): Selection of Doses

BMS-986183 dose escalation (Part 1) will be conducted using an mTPI design. The decision governing when to escalate will follow the mTPI algorithm based on incidence of DLTs (Figure 3.1.1.1-1). The decision on what increment to increase the dose is based on DLTs, AEs, and PK and is explicitly described in Figure 3.1.1.1-2. In the mTPI design 1 to 2 subjects will be enrolled in each dose level cohort (up to 3 cohorts) until the first DLT is observed. Once the first DLT is observed or after the first 3 dose level cohorts with no DLT observed, then at least 3 subjects will be enrolled in each subsequent dose level cohort (including the current cohort).

The first dose level cohort will receive a starting dose of 3 mg (0.05 mg/kg based on a 60 kg body weight individual). This dose may produce ADC exposures below those projected for the human efficacious dose range for BMS-986183 (ie, 0.12 to 3.9 mg/kg and an ADC $AUC_{(0-\infty)} = 189$ to 7,804 µg•h/mL). In addition, in the event that target-mediated drug disposition is observed for this compound, ADC exposures may be even lower than these target exposures. Therefore, dose escalation for each subsequent cohort of subjects will be guided first by the incidence of DLTs/AEs as graded by National Cancer Institute (NCI) Common Terminology Criteria for Adverse Events (CTCAE) version 4.03 (NCI CTCAE v4.03) in the first 3 weeks of dosing (DLT evaluation period) and then by available ADC exposure data.

Dose escalations based upon ADC exposure data:

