In the absence of DLTs or AEs at the starting dose and in the initial dose level cohorts (1 to 2 subjects in the first 3 cohorts; at least 3 subjects in cohort 4 and subsequent cohorts), ADC exposure data will be used to guide dose escalations up to a maximum of 3-fold as long as exposures fall well below the safety margin (ie, active ADC $AUC_{(0-168h)} = 842 \ \mu g \cdot h/mL$)

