determined for the HNSTD (1 mg/kg from the repeat-dose monkey toxicology study). A Bayesian model relating ADC exposure to dose will be derived to guide the next dose level selection. The prior information for the model is based upon target exposures derived from preclinical data (see Appendix 3 and Section 1.1.5.1 for details). Probabilities of ADC exposure at the next dose level will be calculated based upon both the prior information and actual PK data collected in the clinical study. The following criteria will be used to decide if the next dose level can be increased up to a maximum of 3-fold but within the safety margin: 1) the 90% quantile of the predicted next dose level exposure is less than the safety margin; 2) the 90% quantile of the predicted next dose level exposure is less than the target exposure; 3) the next dose level is no more than a 3-fold increase from the current dose level. The first criterion ensures with 90% probability that the next dose level exposures fall below the safety margin. In addition, a CV of 30% will be incorporated into the Bayesian model to ensure that as the dose levels increase, the distribution of next dose level exposures becomes wider and more likely to cover the safety margin, therefore making it less likely to allow dose escalations up to a maximum of 3-fold at higher doses. Once the next dose level exposures are near the safety margin or there is a first occurrence of DLTs/AEs, 3-fold increments will cease and further dose escalations will be based upon mTPI and modified Fibonacci as described previously. Of note, in the absence of DLTs or AEs at the starting dose and in the initial dose level cohorts and in the event that ADC exposure data are not available (e.g. samples weren't drawn at the site or there are significant delays in sample shipping) the next dose level will be a 2-fold increase from the current dose level. See Figure 3.1.1.1-2 for a summary of the decision rules for choice of dose-escalation increments, including use of PK. More details and operating simulation results illustrating the Bayesian model approach are provided in Appendix 3.

Intermediate doses may also be evaluated by safety, PK, and pharmacodynamic if agreed upon by the Sponsor/medical monitor and investigators. If there are dose levels with insufficient data to characterize BMS-986183 monotherapy PK, additional subjects may be enrolled at that dose level upon agreement of the Sponsor/medical monitor and investigators.

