APPENDIX 3 PHARMACOKINETIC-GUIDED DOSE ESCALATION ALGORITHM AND OPERATING CHARACTERISTICS

In the event that there are no dose-limiting toxicities or relevant adverse events in the initial dose cohorts and pharmacokinetic (PK) data are available and informative, a Bayesian model for exposure versus dose will be fit to the accrued data, and Bayesian posterior probabilities will be derived to guide the next dose selection. To illustrate the methodology, the model discussed in this appendix is assumed to be linear, although the final parametric model may be adjusted to account for nonlinearity in PK, which may occur in the event of target-mediated drug disposition. The prior for the model is informative and based on preclinical animal models (details below). Posterior probabilities of exposure at the next dose are calculated based on the prior and actual data collected in the study. If the posterior probability of exposure meets the prespecified criteria (see below), then the prespecified dose will be used in the next cohort; otherwise, a new dose will be calculated using PK data.

To illustrate the methodology, the PK endpoint used in this model is the area under the concentration-time curve from time 0 to infinity (AUC[0, ∞]); however, depending upon the available PK data, other endpoints such as the maximum observed serum and/or plasma concentration (C_{max}) can also be used. From Section 1.1.5.1 in the protocol, the human projected AUC(0, ∞) is 79 µg•h/mL at the starting dose of 0.05 mg/kg (equivalent to 3 mg in a 60-kg individual). Assuming linear PK, the target area under the concentration-time curve as function of dose follows a linear model with a slope B of 1,580. Then the Bayesian linear model takes the form

1) Exposure ~ $B \cdot dose + \sigma(dose)$,

 $B \sim Normal(\mu = 1,580, 316.2)$

 $\sigma(\text{dose}) = 0.30 \cdot \mu \cdot \text{dose} (\text{CV of } 30\%)$

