An informative prior is chosen for the slope B because of limited data in the first few cohorts. Also relevant in the decision rules is the safety margin derived from the repeat-dose monkey study (Section 1.1.5.1 in the protocol). The highest nonseverely toxic dose from that study is 1 mg/kg with an area under the concentration-time curve from 0 to 168 hours of 842 μ g•h/mL. Then, after updating the Bayesian model with the observed data to date and assuming no dose-limiting toxicities or relevant adverse events are observed to date, the following criteria for the next dose will be used to decide if the dose can be increased beyond the default 2-fold increase:

2) Posterior probability of next dose exposure > safety margin is less than 10%, AND

90% quantile of posterior next dose exposure < target exposure, AND

Next dose is \leq 3-fold increase from the current dose

If 2) holds for a dose that is beyond the default 2-fold increase, then that dose may be chosen for the next dose cohort; otherwise, the next dose will default to 2-fold increase.

Simulations were conducted to understand the operating characteristics of the PK-guided dose escalation algorithm. Two scenarios were considered: 1) exposures at each dose match the target exposures (79 μ g•h/mL at the starting dose of 0.05 mg/kg, and then 2-fold increases in dose and

exposure), and 2) exposures at each dose are lower than expected, specifically one-half the level of the target exposures. See Figure 1.

Software for the Bayesian model was written in R v3.2.2 and OpenBugs v3.2.3. Markov chain Monte Carlo was used to fit the model. Twenty simulated trials were generated. Under Scenario 1

Scenarios

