(red line), 50% of the trials allowed at least one 3-fold dose increase and 35% allowed two 3-fold dose increases. All 3-fold dose increases occurred in the first 2 escalations. Under Scenario 2 (green line), 100% of the trials allowed two 3-fold increases, all in the first 2 escalations. Note that with a coefficient of variation of 30%, the standard deviation of exposure increases with dose. With increasing dose, the posterior distribution of the next dose exposure therefore becomes wider and more likely to cover the safety margin. It becomes less likely to allow dose escalations beyond 2-fold at higher does. These simulations indicate that the PK-guided dose-escalation model, while safeguarding against high exposures, allows greater increases in dose and achieves accelerated escalation decisions, especially at lower doses.

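### Protocol Appendix 3's Scenario 1 result (50% and 35% of simulated trials with 3-fold dose steps) does not follow from the criteria written there; one fallback sentence in Section 3.1.1.1 also needs reconciling

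*Protocol*

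**What the plan says.** Appendix 3 of the Protocol sets out a Bayesian model of exposure against dose for Part 1. It is used to decide whether the next dose may rise by more than the default 2-fold. Under linear PK, "the target area under the concentration-time curve as function of dose follows a linear model with a slope B of 1,580". One of the three conditions for a larger step is "90% quantile of posterior next dose exposure < target exposure". The others are a posterior probability under 10% of exceeding the safety margin (842 µg·h/mL) and a cap at 3-fold.

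Twenty trials were simulated. In Scenario 1, "exposures at each dose match the target exposures"; the result is that "50% of the trials allowed at least one 3-fold dose increase and 35% allowed two 3-fold dose increases". In Scenario 2 true exposure is half the target, and all trials are said to allow two 3-fold steps. The appendix concludes that the algorithm speeds escalation while guarding against high exposure.

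The early cohorts are small: "1 to 2 subjects in the first 3 cohorts" (Section 3.1.1.1).

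On what happens when a 3-fold step is not allowed, Section 3.1.1.1 says "Once the next dose level exposures are near the safety margin or there is a first occurrence of DLTs/AEs, 3-fold increments will cease". From then on it hands over to the mTPI rules with modified Fibonacci increments. The first such step is at most +67%. The same section, under escalation based on DLTs/AEs, says increments are up to 2-fold if exposure is not below the stated limits. Appendix 3 also defaults to 2-fold.

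**The concern.** In Scenario 1 the truth equals the target. The 90% quantile of a distribution centred near the target lies above the target, so the target condition should normally block a 3-fold step. Yet half the simulated trials are reported to have taken one.

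This is a first-in-human study, and these 20 trials are the evidence given for the algorithm's behaviour. If the text is followed, the acceleration claimed for Scenario 1 will hardly ever happen. If the code is followed, a more permissive rule than the one in the Protocol would be choosing doses. A reader cannot tell which rule the percentages describe.

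The fallback matters because the same data, with no DLT or AE, could lead to two different maximum next doses.

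**Working it through.** **Inputs (Appendix 3 unless noted).** Target slope 79/0.05 = 1,580. Prior for slope B: Normal, mean 1,580, with 316.2 read as an SD (20% of the mean). Residual SD per unit dose: 0.30 × 1,580 = 474. Margin 842. Start 0.05 mg/kg. True slope 1,580 (Scenario 1) or 790 (Scenario 2). The simulated cohort size is not stated; 1 and 2 are the planned sizes (Section 3.1.1.1), and 3 and 6 were added.

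**Plan's figure.** 50% and 35% of 20 trials are 10/20 and 7/20, with exact 95% limits 27–73% and 15–59%.

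**Rule.** After N subjects in total, the posterior SD of B is s, with 1/s² = 1/316.2² + N/474², and the posterior mean is m. Dose cancels from the target condition, which becomes:
- mean exposure: m + 1.2816·s < 1,580
- individual predicted exposure: m + 1.2816·√(s² + 474²) < 1,580

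**First decision, data exactly as expected (m = 1,580).**
- 1 subject: s = 263.0, so the 90% quantile is 1.21 × target (mean) or 1.44 × target (predictive).
- 2 subjects: s = 230.0, giving 1.19 × and 1.43 ×.

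Both fail.

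**What a 3-fold step would need, 1 subject, mean reading.** The posterior mean must be below 1,580 − 1.2816 × 263.0 = 1,243. The weight on the data is 263.0²/474² = 0.308, so the observed slope must be below 1,580 − 337/0.308 ≈ 485, or 31% of the truth. That is (485 − 1,580)/474 = −2.31 SD, a chance of about 1%. On the predictive reading the observed slope would have to be negative.

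**Full sequence.** Four escalations, 3-fold if all conditions hold and otherwise 2-fold, 200,000 trials per setting:

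| Subjects per cohort | Scenario 1, predictive: ≥1 / two | Scenario 1, mean: ≥1 / two | Scenario 2, mean: two |
|---|---|---|---|
| 1 | 0% / 0% | 3.7% / 0.5% | 10–25% |
| 2 | 0% / 0% | 7.1% / 1.5% | 68–84% |
| 3 | 0% / 0% | 9.0% / 2.2% | 88–99% |
| 6 | 0% / 0% | about 12% / 3% | – |
| Reported | 50% / 35% | 50% / 35% | 100% |

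The Scenario 2 ranges depend on whether scatter is 30% of the target or of the halved mean. On the predictive reading, two 3-fold steps occur in at most about 2% of Scenario 2 trials with 1 to 2 subjects.

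**Noise.** At a true rate of 9%, the chance of 10 or more of 20 is about 3 in a million. At 11.8% it is about 3 in 100,000.

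**Variants, Scenario 1.** A vague prior gives at most 16% / 5%. Drawing the true slope from the prior, with 1 to 2 subjects, gives at most 18% / 7%. A fixed target of 189 gives 0% / 0%. A fixed target of 7,804 gives 100% with at least one step.

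**Fallback.** With 2-fold steps only, the doses are 3, 6 and 12 mg. From 12 mg, a 3-fold step to 36 mg (0.6 mg/kg) projects 1,580 × 0.6 = 948, above 842, so it is not allowed. The next dose (level 4) is then:
- 2-fold: 24 mg (0.4 mg/kg), projected AUC 632, about 15% predicted chance above 842
- +67%: 12 × 1.67 ≈ 20 mg, projected AUC about 528, about 3%

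**The case against.** **This may be a reporting gap and not an error.** Section 1.1.5.1, Appendix 3 Figure 1 and Figure 3.1.1.1-2 are not in the public text. The cohort size and the type of exposure simulated are unstated, and the appendix calls its linear model an illustration. Section 3.1.1.1 also uses the word target for a wider efficacious range ("ADC exposures may be even lower than these target exposures"). Its ends imply slopes of 189/0.12 = 1,575 and 7,804/3.9 ≈ 2,001. On mean exposure with 2 subjects, a target 15% above 1,580 gives about 55% / 29%, close to the report. This stands in part: the result is very sensitive to the target, and a different target may have been coded. But Appendix 3 documents 1,580, and neither end of the range fits on the mean reading with 2 subjects: 1,575 gives 6.6% / 1.4% and 2,001 gives 91.7% / 58.1%.

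A reader might infer which rule was run, such as a higher target or a median in place of the 90% quantile. The documents do not identify it.

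**The fallback may not conflict between sections.** A reader might infer that Section 3.1.1.1 and Appendix 3 simply prescribe different next doses. They do not: the DLT/AE paragraph of Section 3.1.1.1 gives the same up-to-2-fold rule as Appendix 3. The conflict is with one sentence, whose closeness to the margin is undefined and is not stated to mean failure of the 10% criterion. The missing decision tree may settle it. A larger dose gap can be built from a path that includes a 3-fold step, but in Scenario 1 the written rule almost never allows one.

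**The consequence is small.** The percentages set no sample size, dose or endpoint, and DLT and mTPI rules still govern escalation. That stands.

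**Conclusion.** The main point holds. At the documented target, the written criteria give about 0% / 0% (individual predicted exposure) or about 4–9% / 0.5–2% (mean exposure, 1 to 3 subjects), against the reported 50% / 35%. The gap is far beyond 20-trial noise, so the rule simulated was not the rule written. The Scenario 2 mismatch is weaker evidence. It is clear on the predictive reading and with 1 subject; on the mean reading with 2 subjects at 84%, 20 of 20 would still occur about 3% of the time (0.84^20).

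The fallback point is secondary: one sentence is inconsistent with the rest of its own section and with Appendix 3. In the 2-fold-only path it affects one step, 24 mg or about 20 mg at level 4.

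A reader might infer that subjects face unsafe doses. The documents do not support that: the written rule is stricter than the reported figures suggest, and the DLT/AE and mTPI rules remain. What is lost is the support for the stated operating characteristics.

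Assumptions: 316.2 is an SD; AUC to infinity is compared directly with the 0–168 h margin, as Appendix 3 does, which is conservative; and the sections and figures not visible do not redefine the target. Confidence is medium for that last reason.

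**What to change.** 1. State once, for both Section 3.1.1.1 and Appendix 3, which exposure the criteria use (individual predictive or mean), which AUC metric (matched to the 842 margin) and which target.
2. Make the code and the text agree, then re-run with 1 to 2 subjects in the early cohorts and enough trials for stable percentages. At a rate of 50%, 1,000 trials give a standard error of √(0.25/1,000) = 1.6 percentage points; 20 trials give 11.
3. Replace the 50%, 35% and 100% figures and the conclusion drawn from them.
4. State one fallback rule, define closeness to the safety margin and the proposed dose at which it is tested, and check the rule against Figure 3.1.1.1-2.

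The cost is a short re-simulation with existing code and a wording change. It needs no extra subjects by design. If the smaller step is chosen, early escalation near the margin is slightly slower.

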APPENDIX 6 RECIST V1.1

This Appendix has been excerpted from the full Response Evaluation Criteria in Solid Tumors Version 1.1 (RECIST v1.1).¹ For information pertaining to RECIST v1.1 not contained in the study protocol or in this Appendix, please refer to the full publication.¹

1 ASSESSMENT OF OVERALL TUMOR BURDEN AND MEASURABLE DISEASE

To assess objective response or future progression, it is necessary to estimate the overall tumor burden at baseline and use this as a comparator for subsequent measurements. Measurable disease is defined by the presence of ≥ 1 measurable lesion.

1.1 Measurability of Tumor

At baseline, tumor lesions/lymph nodes will be categorized measurable or nonmeasurable as follows. All baseline evaluations should be performed as close as possible to the treatment start and never more than 4 weeks before the beginning of the treatment.

Measurable lesions must be accurately measured in at least 1 dimension (longest diameter in the plane of the measurement to be recorded) with a minimum size of:

- 10 mm by computed tomography (CT) scan (CT scan slice thickness \leq 5 mm)
- 10 mm caliper measurement by clinical examination (lesions that cannot be accurately measured with calipers should be recorded as nonmeasurable)
- 20 mm by chest x-ray
- Malignant lymph nodes: To be considered pathologically enlarged and measurable, a lymph node must be ≥ 15 mm in short axis when assessed by CT scan (CT scan slice thickness recommended to be ≤ 5 mm). At baseline and in follow-up, only the short axis will be measured and followed.

All measurements should be recorded in metric notation, using calipers if clinically assessed.

Special considerations regarding lesion measurability

Bone lesions:

- Bone scan, positron emission tomography scan or plain films are not considered adequate imaging techniques to measure bone lesions. However, these techniques can be used to confirm the presence or disappearance of bone lesions.
- Lytic bone lesions or mixed lytic-blastic lesions, with identifiable soft tissue components, that can be evaluated by cross-sectional imaging techniques such as CT or magnetic resonance imaging (MRI) can be considered as measurable lesions if the soft tissue component meets the definition of measurability described above.
- Blastic bone lesions are nonmeasurable.

Cystic lesions:

- Lesions that meet the criteria for radiographically defined simple cysts should not be considered as malignant lesions (neither measurable nor nonmeasurable) since they are, by definition, simple cysts.
- 'Cystic lesions' thought to represent cystic metastases can be considered as measurable lesions if they meet the definition of measurability described above. However, if noncystic lesions are present in the same patient, these are preferred for selection as target lesions.

Lesions with prior local treatment:

• Tumor lesions situated in a previously irradiated area, or in an area subjected to other loco-regional therapy, are usually not considered measurable unless there has been demonstrated progression in the lesion.

Nonmeasurable lesions are all other lesions, including small lesions (longest diameter < 10 mm or pathological lymph nodes with ≥ 10 to < 15 mm short axis), as well as nonmeasurable lesions. Lesions considered nonmeasurable include leptomeningeal disease, ascites, pleural or pericardial effusion, inflammatory breast disease, lymphangitic involvement of skin or lung, and abdominal masses/abdominal organomegaly identified by physical examination that is not measurable by reproducible imaging techniques.

1.2 Method of Assessment

The **same method of assessment and the same technique should be used** to characterize each identified and reported lesion at baseline and during follow-up. Imaging-based evaluation should always be performed rather than clinical examination unless the lesion(s) being followed cannot be imaged but are assessable by clinical examination.

CT, MRI: CT is the best currently available and reproducible method to measure lesions selected for response assessment. Measurability of lesions on CT scan is based on the assumption that CT slice thickness is 5 mm or less. When CT scans have slice thickness > 5 mm, the minimum size for a measurable lesion should be twice the slice thickness.

Chest x-ray: Chest CT is preferred over chest x-ray, particularly when progression is an important endpoint since CT is more sensitive than x-ray, particularly in identifying new lesions. However, lesions on chest x-ray may be considered measurable if they are clearly defined and surrounded by aerated lung.

Clinical lesions: Clinical lesions will only be considered measurable when they are superficial and ≥ 10 mm diameter as assessed using calipers. For the case of skin lesions, documentation by color photography including a ruler to estimate the size of the lesion is suggested. As noted above, when lesions can be evaluated by both clinical examination and imaging, imaging evaluation should be undertaken since it is more objective and may be reviewed at the end of the study.

Ultrasound: Ultrasound is not useful in the assessment of lesion size and should not be used as a method of measurement. If new lesions are identified by ultrasound in the course of the study, confirmation by CT or MRI is advised.

Endoscopy, laparoscopy: The utilization of these techniques for objective tumor evaluation is not advised.

Tumor markers: Tumor markers alone cannot be used to assess objective tumor response.

